8.10 Early Discontinuation of Study Treatment

A subject will be considered to have completed the efficacy portion of the trial if they received at least 21 days of treatment with study drug or the subject has been discharged from the hospital, or the subject has expired or the study is terminated by the sponsor. Subjects may prematurely discontinue study treatment for any of the following reasons:

- 1. Consent Withdrawn (specify the reason).
- 2. Significant and unacceptable adverse event specify the adverse event leading to discontinuation
- 3. Investigator decision (specify the reason), must be approved by the Medical Monitor
- 4. Non-compliance by subject with protocol requirements, must be approved by the Medical Monitor
- 5. Lost to follow-up (record the date of last contact)
- 6. Death (specify the following information)
 - a. Date of death
 - b. Death due to primary disease? Yes or no
 - c. Death due to study drug? Yes or no
 - d. Death due to adverse event? Yes or no
- 7. Study terminated by the Sponsor
- 8. Other reason (specify the reason) should be approved by the Medical Monitor

The reason for discontinuation of study treatment will be documented for each subject. Subjects who discontinue prematurely will not be replaced. If a subject is discontinued from the study, he will be asked to complete all End of Study visit assessments and return all study materials (study medication and electronic device). At the time of discontinuation, please fill out the End of Study case report forms (eCRFs) and subject disposition eCRF pages.

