5.2 Study Duration

The study will require that each subject in the VERU-111 treated groups receive 18 mg daily oral dose of VERU-111 or placebo for up to 21 days (Day 21) with final on study efficacy assessments done on Day 29 with safety assessments continuing to Day 60 of the study. The total duration of the study for a subject in the study from screening to follow-up visit (approximately Day 60 on study) will be approximately 62 days.

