8.2 Enrollment

Enrollment should be done after the subject has completed the screening assessments and after it has been determined that the subject meets all the inclusion and exclusion criteria.

Subject will be randomized into one of two treatment groups.

8.3 Day 1

The Day 1 visit assessments will serve as the baseline assessments.

- 1. The medical history should be reviewed and updated to include any changes occurring since the screening visit. This will include the following:
 - a. Number of days from onset of COVID-19 symptoms to Day 1

- b. Specific reason for hospitalization
- 2. Assessment of eligibility
- 3. Vital signs (temperature/pulse/supine, if possible, blood pressure)
- 4. SpO_2
- 5. Physical examination (including weight)
- 6. Chest X-ray or Computed Tomography (CT) scan
- 7. Clinical Laboratory Tests
 - a. Hematology (Appendix A)
 - b. Serum chemistry (Appendix A)
 - c. Urinalysis
- 8. Record the usage of any concomitant medications and ongoing treatments.
- 9. Adverse events (ongoing on Day 1)
- 10. First dose of study drug
- 11. Temperature and SpO₂ every 12 hours after dosing

8.4 Day 2 through Day 21

The following assessments will be conducted on each of Day 2 to Day 21

- 1. Temperature and SpO₂ every 12 hours
- 2. Vital signs (temperature/pulse/supine, if possible, blood pressure)
- 3. Record the usage of any concomitant medications and ongoing treatments. This should include the following:
 - a. Documentation of the standard of care
 - b. The clinical rationale for initiation of mechanical ventilation, if necessary
 - c. Documentation of supportive measures for ARDS (e.g., proning, paralytics, etc.)
 - d. Care decisions that are based on limitations of resources at the clinical site
- 4. Adverse events
- 5. Dose study drug
- 6. At the time of discharge from the hospital, patients should be advised to use refrain from prolonged exposure to the sun or use at least SPF 50 on all exposed skin and protective clothing during prolonged sun exposure until the Day 60 adverse event assessment.

8.5 Day 3, Day 9, and Day 15

The following additional assessment will be conducted on Days 3, Day 9 and 15:

- 1. Serum Chemistry (Appendix A)
- 2. Hematology (Appendix A)
- 3. Assessment of primary and secondary endpoints (Day 15 only)
- 4. Physical examination (including weight) (Day 15 only)
- 5. 12 lead ECG (single) (Day 15 only)
- 6. Pregnancy test (Day 15 only)

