8.7 Day 29 ± 3 days

The following assessments will be performed at approximately Day 29 (\pm 3 days):

- 1. Vital Signs (temperature/pulse/supine blood pressure)
- 2. SpO₂
- 3. Physical examination (including weight)
- 4. 12-lead ECG (single)
- 5. Chest X-ray or CT scan
- 6. Clinical Laboratory tests
 - a. Hematology (Appendix A)
 - b. Serum chemistry (Appendix A)
 - c. Urinalysis
- 7. Adverse events
- 8. Record the usage of any concomitant medications and ongoing treatments.
- 9. Assessment of primary and secondary endpoints
- 10. Pregnancy test

8.8 Follow up visits at Day 45 (± 3 days) and Day 60 (± 3 days) (can be conducted via phone/teleconference)

- 1. Adverse events
- 2. Assessment of primary and secondary endpoints (observational assessment)

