# 6.12.1 Primary Endpoint

QMD Ref: Worldwide-TMP-ST-005-7.0 Effective: 12Aug2019 Governing QMD: Worldwide-SOP-ST-		
Confidentiality Statement		
This document is the property of Worldwide Clinical Trials Inc. and may not be duplicated, copied, altered or removed from company without prior approval from Worldwide Quality Assurance or in compliance with Worldwide Standard Operating Procedures.		

REF: Worldwide-TMP-QA-001f-1.3

Worldwide Clinical Trials Controlled Quality Management Document		
WORLDWIDE CLINICAL TRIALS	Sponsor:	Veru Inc.
	Protocol Number:	V0211901
STATISTICAL ANALYSIS PLAN. PHASE 2-3-4		

The primary endpoint for the study is the proportion of subjects that are alive without respiratory failure at Day 29. Respiratory failure is defined as endotracheal intubation and mechanical ventilation, extracorporeal membrane oxygenation, high-flow nasal cannula oxygen delivery, noninvasive positive pressure ventilation, clinical diagnosis of respiratory failure with initiation of none of these measures only when clinical decision making is driven solely by resource limitation.

This analysis will compare the percentage of subjects that are alive without respiratory failure on Day 29 (responder).

Responders are subjects who have Grade 0-4 on the WHO Ordinal Scale for Clinical Improvement on Day 29. If subject was discharged from the hospital prior to Day 29 and WHO Ordinal Scale for Clinical Improvement is not collected at Day 29 then the last available observation before or at the time of discharge will be carried forward.

Non-responders are subjects who died before Day 29 or has Grade 5, 6, 7, or 8 on the WHO Ordinal Scale for Clinical Improvement on Day 29.

The number and percentage of responders will be summarized by treatment group. Responders will be analyzed using a logistic regression model. This model will include treatment as a factor, and study site, remdesivir use (No/Yes), dexamethasone use (No/Yes) and WHO Ordinal Scale for Clinical Improvement at baseline as a covariates. Odds ratios, standard errors, 95% confidence intervals and p-values for the treatment difference will be presented.

The primary analysis will be performed on the ITT population. A sensitivity analysis will be performed repeating the analysis on the EE population.

Example SAS code for the analysis is as follows:

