#### **6.12.2** Secondary Endpoints

# 6.12.2.1 Change in mean WHO Ordinal Scale for Clinical Improvement at Day 15, Day 22 and Day 29

The mean change in WHO Ordinal Scale for Clinical Improvement from baseline to Day 15, Day 22 and Day 29 will be assessed.

Baseline for WHO Ordinal Scale is the last available record up to and including Day 1. If subject died or was discharged from the hospital prior to Day 15, 22 or 29 and WHO Ordinal Scale for Clinical Improvement is not collected or record is otherwise missing at those timepoints then the last available observation before or at the time of death/discharge will be carried forward.

Analysis will be performed using two different approaches, including the LOCF values and excluding LOCF values. Further, these analyses will be repeated using separate baseline definition. As the time of WHO Ordinal Scale is collected it cannot be definitely confirmed if Day 1 record was taken before or after start of study treatment. Sensitivity analysis will be performed using the WHO Ordinal Scale from Screening record.

Descriptive statistics (n, mean, standard deviation, median, minimum and maximum) will be summarized for absolute values and change from baseline by treatment group and visit.

Change from baseline will be analyzed using mixed model for repeated measures (MMRM) including treatment, visit and treatment-by-visit interaction as fixed effects, and study site, remdesivir use (No/Yes), dexamethasone use (No/Yes) and WHO Ordinal Scale for Clinical Improvement at baseline as covariates. The resulting F-tests will be based on Kenward-Roger's adjusted degrees of freedom. Subject effect will be assumed to be random and an unstructured covariance structure will be used for within subject variation. If this model does not converge then the following covariance matrices will be used in order until the model converges: Toeplitz, first-order autoregressive, and compound symmetry. Least squares means, standard errors, 95% confidence intervals and p-values for treatments and treatment differences at each visit (study days 15, 22, 29, 45 and 60) will be presented.

QMD Ref: Worldwide-TMP-ST-005-7.0 Effective: 12Aug2019 Governing QMD: Worldwide-SOP-ST-0		
Confidentiality Statement		
This document is the property of Worldwide Clinical Trials Inc. and may not be duplicated, copied, altered or removed from company without		

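### The protocol ends the efficacy portion at discharge or after 21 days of drug and schedules no WHO score at discharge, so WHO-based outcomes for discharged patients, including the primary endpoint, can rest on a stale carried-forward score

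*Protocol*

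**What the plan says.** Protocol 8.10 counts the efficacy portion as complete "if they received at least 21 days of treatment with study drug or the subject has been discharged from the hospital"; death and termination of the study by the sponsor also complete it. Protocol 5.2 instead has "final on study efficacy assessments done on Day 29". Sections 8.5 to 8.7 and Appendix B place endpoint assessments at Days 15, 22 and 29 and make no exception for patients who have gone home.

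The only action that Protocol 8.4 ties to discharge is advice about sun exposure. The Day 22 assessments are repeated at early termination or discontinuation from the study (8.6), but discharge is not named there. Visits at Days 45 and 60 "can be conducted via phone/teleconference" (8.8). No such allowance appears for Days 15, 22 or 29.

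For the primary endpoint, SAP 6.12.1 says that if a patient was discharged before Day 29 and has no Day 29 score, "then the last available observation before or at the time of discharge will be carried forward". SAP 6.12.2.6 repeats the primary analysis at Days 15 and 22. For WHO change, SAP 6.12.2.1 has the matching rule: "then the last available observation before or at the time of death/discharge will be carried forward".

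**The concern.** A site that follows 8.10 could regard a patient discharged on Day 10 as finished for efficacy, and nothing in the visit lists asks it to score that patient on leaving. The Day 22 and Day 29 visits list ECG, chest imaging and laboratory tests, which a patient at home may not attend. The SAP then fills the gap with whatever score was last recorded.

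The outcomes at stake are those built on the WHO scale: alive without respiratory failure at Days 15, 22 and 29, and change in WHO score. The first of these at Day 29 is the primary endpoint. The protocol's design summary ties the move to Phase 3 to the same outcome at Day 22, where the same carry-forward rule applies.

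**Working it through.** **Inputs**

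- Responder: WHO 0-4 on Day 29. Non-responder: WHO 5-8 on Day 29, or death before Day 29 (SAP 6.12.1).
- Baseline WHO 5 is eligible, and so is WHO 6 for less than five days (Protocol 6.2.2).
- About 40 patients, 20 per arm (Protocol 6.1, SAP 5).
- Neither document gives a power calculation (Protocol 9.1, SAP 4), an assumed response rate, discharge timing or Day 29 attendance. There is no plan figure to reproduce, so the rates below are assumptions.

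**Step 1: trace the rule.** Take two hypothetical patients, neither with a Day 29 score.

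| Patient | Score carried | Primary result | True Day 29 status |
|---|---|---|---|
| A: baseline 5, home on Day 10, well | 5 (baseline is the last score) | Non-responder | Responder |
| A, same course | 3 or 4 (late inpatient) | Responder | Responder |
| A, same course | 2 (scored on leaving) | Responder | Responder |
| B: left with last score 4, later readmitted on high-flow oxygen | 4 | Responder | Non-responder |

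In the first row, patient A is also a responder for alive and discharged from hospital (SAP 6.12.2.8), so two endpoints would disagree about the same patient.

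**Step 2: size per patient.** 1/20 = 5 percentage points in that arm's rate.

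**Step 3: illustration.** Assume true counts of 18/20 on active drug and 12/20 on placebo. I use the pooled-variance Wald test, as in the SAP's responder-rate code; the logistic model cannot be reproduced from counts alone.

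z = (p1 − p0) / √[p̄(1 − p̄) × 2/20], with p̄ = (x1 + x0)/40.

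| Discharged responders carried as 5-6 | Counts | Difference | z | p |
|---|---|---|---|---|
| None | 18 v 12 | 30 points | 0.30/0.137 = 2.19 | 0.029 |
| One, active | 17 v 12 | 25 points | 0.25/0.141 = 1.77 | 0.077 |
| Two, active | 16 v 12 | 20 points | 0.20/0.145 = 1.38 | 0.168 |
| One, placebo | 18 v 11 | 35 points | 0.35/0.141 = 2.48 | 0.013 |

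Under these assumptions, one patient is enough to move p across 0.05, and the direction depends on the arm.

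**Step 4: WHO change.** A true move from 4 to 1 is 1 − 4 = −3. Carrying the baseline gives 4 − 4 = 0; carrying an inpatient 3 gives 3 − 4 = −1. If a share f of an arm has the baseline carried and the true change is c, the arm's mean improvement is understated by f × |c|. For assumed f of 25% to 75% and c of −2 to −3, that runs from 0.25 × 2 = 0.5 to 0.75 × 3 = 2.25 points.

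**Step 5: would a planned analysis show it?** WHO change is run with and without carried values (SAP 6.12.2.1). The primary endpoint has only the EE repeat and the responder-rate differences (SAP 6.12.1), and neither changes how a discharged patient is scored. Protocol 9.3.1 would exclude patients whose Day 29 status cannot be established and count them as non-responders in a sensitivity analysis. The SAP has neither step and does not list the change in its section 9.

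**The case against.** The strongest reply is that the visit lists are not a full record of when the WHO scale was scored. They contain no WHO assessment at Screening or Day 1 either, yet SAP 6.12.2.1 relies on records from both. Protocol 9.4.1.2 refers to the worst category on each day. SAP 6.12.3.1 uses all available scores up to Day 15 and gives an example of a patient who leaves with a score of 2 on Day 5. The carry-forward rule also covers a score taken at discharge itself. A reader might infer that the baseline score must be what is carried for anyone home before Day 15, or that the last score before leaving is always 3 or higher. The documents do not support either.

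It is also fair that follow-up does not formally stop at discharge. The 8.10 sentence sits under discontinuation of treatment, and endpoint visits are still scheduled through Day 29. Carry-forward applies only when a visit score is missing. On the primary endpoint, carrying a 3 or 4 for a patient who stays well changes nothing.

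What remains is that the protocol nowhere requires the discharge score on which the SAP's example depends. SAP 6.2.9 disregards unscheduled post-baseline values in tables, which leaves it unclear whether an extra discharge score would count. The wording of 8.10 still conflicts with 5.2.

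**Conclusion.** The point holds as a gap between the two documents that should be closed. For a discharged patient with no later record, the plan permits a stale pre-discharge score, possibly the baseline one, to decide the primary endpoint. Each patient misclassified this way is worth 5 points at 20 per arm. The frequency is unknown because the eCRF schedule, discharge timing and Day 29 attendance are not given. The p-values above rest on assumed counts and only show sensitivity.

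Two broader conclusions are tempting but unsupported. A reader might infer that the rule hides a real benefit. In fact a carried 5 or 6 creates false failures in whichever arm it occurs, and a carried 3 or 4 can create false responses. A reader might also infer that all outcomes from Day 15 to Day 29 are affected. Mortality and the ICU and hospital discharge endpoints have their own definitions, a known death before Day 29 is a non-response on the primary endpoint whatever score was last recorded, and WHO change already has an analysis without carried values. The primary endpoint has no such analysis.

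**What to change.** 1. Reconcile Protocol 8.10 with 5.2: discharge or 21 days of drug completes dosing only, and the efficacy portion ends at the Day 29 status assessment or death. The dosing rule itself is unchanged.
2. Add a WHO score at discharge, reflecting status on leaving, to Protocol 8.4 and Appendix B.
3. In Protocol 8.5 to 8.7, allow WHO and vital status of discharged patients at Days 15, 22 and 29 to be taken by phone, as 8.8 already does for Days 45 and 60. This matters because even a good discharge score cannot show a later readmission.
4. In the SAP, carry forward only the at-discharge score. If it is missing, treat Day 29 status as unknown and handle it as in Protocol 9.3.1: exclude, with a non-responder sensitivity analysis. Add a primary-endpoint sensitivity analysis that uses no carried scores.

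The cost is wording in both documents, one eCRF field, up to three short calls per discharged patient and a few extra tables. Phone reports are less detailed than a visit. SAP section 9 indicates that all randomized subjects had already been treated, so at that date item 4 was the part that could still be changed, before database lock.

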8.11 Adverse Events

An adverse event (AE) is any unfavorable or unintended change in body structure (signs) or body function (symptoms), abnormal laboratory result that is associated with symptoms or requires treatment or worsening of a pre-existing condition. This includes all such events regardless of the presumed relationship between the event and the study medication(s).

Any AE that occurs after the informed consent is signed but prior to dosing on Day 1 will be captured as part of the medical history and will be documented on the appropriate eCRF. This would include AEs resulting from concurrent illnesses, reactions to concomitant medications or progressive disease states. These AEs will be captured as part of the medical history.

Each subject will be assessed for the development of any adverse events. Adverse events should be assessed at each visit to the clinic. This information should be obtained in the form of non-leading questions (e.g., "How are you feeling?") and from signs and symptoms detected during each examination, observations of the study personnel or spontaneous reports from the subjects.

Any AEs such as complaints, signs, or symptoms that occur during the course of the study or designated follow-up periods will be recorded on the subject's case report form (eCRF). This would include AEs resulting from concurrent illnesses, reactions to concomitant medications, or progressive disease states.

Whenever possible, the AE will be described on the case report form using standard medical terminology consistent with Common Terminology Criteria for Adverse Events (CTCAE) version 4 in order to avoid the use of vague, ambiguous or colloquial expressions. The investigator will evaluate all adverse events as to their intensity, relation to test medication, outcome and action taken.

Each AE will be evaluated for duration, intensity, and relationship to (or association with) the study treatment (or other causes). Additionally, the actions taken (e.g., reduction of dosage, discontinuation of study medication, administration of treatment, etc.) and the resulting outcome of the AE will be indicated on the case report form.

Any subject who is withdrawn from the study due to an adverse event will be followed until the outcome of the event is determined, and the investigator will prepare a written summary of the event and document the available follow-up information on the case report form.

8.11.1 Intensity of Adverse Events

The intensity of the AEs will be graded according to CTCAE version 4. For any adverse event that is not specifically covered in CTCAE version 4, the following criteria should be used:

Grade	Description
1	Mild; asymptomatic or mild symptoms; clinical or diagnostic observations only; intervention not indicated
2	Moderate; minimal, local or noninvasive intervention indicated; limiting age-appropriate instrumental activities of daily living
3	Severe or medically significant but not immediately life-threatening; hospitalization or prolongation of hospitalization indicated; disabling; limiting self-care activities of daily living
4	Life-threatening consequences: urgent intervention indicated.
5	Death related to AE

If the intensity (Grade) changes within a day, the maximum intensity (Grade) should be recorded. If the intensity (Grade) changes over a longer period of time, the changes should be recorded as separate events (having separate onset and stop dates for each grade).

8.11.2 Test Medication Causality

The relationship (or association) of each AE to the test medication will be assessed by the investigator according to the following definitions:

Unrelated: There is no chance that the study medication caused the AE; other conditions, including concurrent illnesses, progression or expression of the disease state, or a reaction to a concomitant medication best explain the event.

Unlikely: There is little chance that the study medication caused the AE; other conditions, including concurrent illnesses, progression or expression of the disease state, or a reaction to a concomitant medication best explain the event.

Possible: The association of the AE with the study medication is unknown; however, the AE is not clearly due to another condition.

Probable: A reasonable temporal association exists between the AE and treatment administration and, based on the investigator's clinical experience, the association of the AE with the study treatment seems likely.

Definite: The association of the AE with the study medication has a direct relationship.

For the purpose of safety analyses, all AEs which are classified as "Possible," "Probable" or "Definite" will be considered treatment-related events.

8.11.4 Initial Reports

SAEs will be collected from the time of first study drug administration through 60 days after first study drug administration. SAEs and events of clinical interest must be reported to the Sponsor (or designee) within 24 hours of the knowledge of the occurrence.

In the event an SAE is observed or reported, the SAE report will be completed as thoroughly as possible including all available details about the event and the signature of the Investigator. If the Investigator does not have all information about an SAE, the Investigator will not wait to receive additional information before notifying the Sponsor of the event and completing the form. The form will be updated when additional information is received.

